8.3 RECORDS

CRFs for individual subjects will be provided by the sponsor. For drug accountability, refer to Section [4.1.8](#).

8.3.1 Source documents

In accordance with regulatory requirements, the investigator should prepare and maintain adequate and accurate source documents and trial records for each trial subject that include all observations and other data pertinent to the investigation. Source data as well as reported data should follow the 'ALCOA principles' and be attributable, legible, contemporaneous, original, and accurate. Changes to the data should be traceable (audit trail).

Data reported on the CRF must be consistent with the source data or the discrepancies must be explained.

Before providing any copy of subjects' source documents to the sponsor, the investigator must ensure that all subject identifiers (e.g., subject's name, initials, address, phone number, and social security number) have properly been removed or redacted to ensure subject confidentiality.

If the subject is not compliant with the protocol, any corrective action (e.g. re-training) must be documented in the subject file.

For the CRF, data must be derived from source documents, for example:

Proprietary confidential information © 2018 Boehringer Ingelheim International GmbH or one or more of its affiliated companies

- Subject identification: sex, year of birth (in accordance with local laws and regulations)
- Subject participation in the trial (substance, trial number, subject number, date subject was informed)
- Dates of subject's visits, including dispensing of trial medication
- Medical history (including trial indication and concomitant diseases, if applicable)
- Medication history
- AEs and outcome events (onset date [mandatory], and end date [if available])
- SAEs (onset date [mandatory], and end date [if available])
- Concomitant therapy (start date, changes)
- Originals or copies of laboratory results and other imaging or testing results, with proper documented medical evaluation (in validated electronic format, if available)
- ECG results (original or copies of printouts)
- Completion of subject's participation in the trial (end date; in case of premature discontinuation, document the reason for it, if known)
- Prior to allocation of a subject to a treatment into a clinical trial, there must be documented evidence in the source data (e.g. medical records) that the trial participant meets all inclusion criteria and does not meet any exclusion criteria. The absence of records (either medical records, verbal documented feedback of the subject or testing conducted specific for a protocol) to support inclusion/exclusion criteria does not make the subject eligible for the clinical trial.

8.3.2 Direct access to source data and documents

The investigator /institution will allow site trial-related monitoring, audits, IRB / IEC review and regulatory inspections. Direct access must be provided to the CRF and all source documents/data, including progress notes, copies of laboratory and medical test results, which must be available at all times for review by the Clinical Research Associate, auditor and regulatory inspector (e.g. FDA). They may review all CRFs and informed consents. The accuracy of the data will be verified by direct comparison with the source documents described in Section [8.3.1](#). The sponsor will also monitor compliance with the protocol and GCP.

8.3.3 Storage period of records

Trial site:

The trial site(s) must retain the source and essential documents (including ISF) according to the local requirements valid at the time of the end of the trial.

Sponsor:

The sponsor must retain the essential documents according to the sponsor's SOPs.

8.4 EXPEDITED REPORTING OF ADVERSE EVENTS

BI is responsible to fulfil their legal and regulatory reporting obligation in accordance with regulatory requirements.

8.5 STATEMENT OF CONFIDENTIALITY AND SUBJECT PRIVACY

Individual subject data obtained as a result of this trial is considered confidential and disclosure to third parties is prohibited with the exceptions noted in Section [8.7](#).

Data protection and data security measures are implemented for the collection, storage and processing of patient data in accordance with the principles 6 and 12 of the WHO GCP handbook.

Personalised treatment data may be given to the subject's personal physician or to other appropriate medical personnel responsible for the subject's welfare. Data generated at the site as a result of the trial need to be available for inspection on request by the participating physicians, the sponsor's representatives, by the IRB / IEC and the regulatory authorities.

8.5.1 Collection, storage and future use of biological samples and corresponding data

Measures are in place to comply with the applicable rules for the collection, storage and future use of biological samples and clinical data, in particular

- Sample and data usage has to be in accordance with the informed consent
- The BI-internal facilities storing biological samples from clinical trial participants as well as the external storage facility are qualified for the storage of biological samples collected in clinical trials.
- An appropriate sample and data management system, incl. audit trail for clinical data and samples to identify and destroy such samples according to ICF is in place
- A fit for the purpose documentation (e.g. biomarker proposal, analysis plan and report) ensures compliant usage
- If applicable, a fit for purpose approach will be used for assay/equipment validation depending on the intended use of the biomarker data

Samples and/or data may be transferred to third parties and other countries as specified in the ICF.

8.6 TRIAL MILESTONES

The start of the trial is defined as the date of the enrolment of the first subject in the trial.

The end of the trial is defined as the 'date of the last visit of the last subject in whole trial' ('Last Subject Completed') or 'end date of the last open AE' or 'date of the last follow-up test' or 'date of an AE has been decided as sufficiently followed-up', whichever is latest.

Proprietary confidential information © 2018 Boehringer Ingelheim International GmbH or one or more of its affiliated companies

Early termination of the trial is defined as the premature termination of the trial for any reason before the end of the trial as specified in this protocol.

Temporary halt of the trial is defined as any unplanned interruption of the trial by the sponsor with the intention to resume it.

Suspension of the trial is defined as an interruption of the trial based on a Health Authority request.

The EC/competent authority in each participating EU member state will be notified about the trial milestones according to the laws of each member state.

A final report of the clinical trial data will be written only after all subjects have completed the trial in all countries (EU or non-EU), so that all data can be incorporated and considered in the report.

The sponsor will submit to the EU database a summary of the final trial results within one year from the end of a clinical trial as a whole, regardless of the country of the last patient (EU or non-EU).

8.7 ADMINISTRATIVE STRUCTURE OF THE TRIAL

The trial is sponsored by Boehringer Ingelheim (BI).

The trial will be conducted at the

, under the supervision of the Principal Investigator. Relevant documentation on the participating (Principal) Investigators (e.g. their curricula vitae) will be filed in the ISF.

BI has appointed a Trial Clinical Monitor, responsible for coordinating all required trial activities, in order to

- Manage the trial in accordance with applicable regulations and internal SOPs
- Direct the clinical trial team in the preparation, conduct, and reporting of the trial
- ensure appropriate training and information of local clinical monitors (CML), Clinical Research Associates, and investigators of participating trial sites

The trial medication will be provided by the Clinical Trial Supplies Unit, BI Pharma GmbH & Co. KG, Biberach, Germany.

Safety laboratory tests will be performed by the local laboratory of the trial site

Analyses of BI 1323495 concentrations in plasma will be performed

On-site monitoring will be performed by BI or a contract research organisation appointed by BI.

Data management and statistical evaluation will be done by BI according to BI SOPs.

Tasks and functions assigned in order to organise, manage, and evaluate the trial are defined according to BI SOPs. A list of responsible persons and relevant local information can be found in the ISF.

10. APPENDICES

Not applicable.

Proprietary confidential information © 2018 Boehringer Ingelheim International GmbH or one or more of its affiliated companies

11. DESCRIPTION OF GLOBAL AMENDMENT(S)

11.1 GLOBAL AMENDMENT 1

Date of amendment	22 November 2018	
EudraCT number	2018-002792-18	
EU number		
BI Trial number	1405-0007	
BI Investigational Medicinal Product(s)	BI 1323495	
Title of protocol	Relative bioavailability of BI 1323495 following oral administration under fed and fasted conditions in healthy male subjects (an open-label, randomised, single-dose, two-period, two-sequence crossover study)	
To be implemented only after approval of the IRB / IEC / Competent Authorities		
To be implemented immediately in order to eliminate hazard – IRB / IEC / Competent Authority to be notified of change with request for approval		
Can be implemented without IRB / IEC / Competent Authority approval as changes involve logistical or administrative aspects only		
Section to be changed	1	Flow Chart
	2	Section 1.2.4 Clinical experience in humans
	3	Section 1.4 Benefit – Risk Assessment
	4	Section 3.3.3 Exclusion criteria
	5	Section 3.3.4.1 Discontinuation of trial treatment
	6	Section 3.3.4.3 Discontinuation of the trial by the sponsor
	7	Section 3.3.5 Replacement of subjects
	8	Section 4.1.3 Method of assigning subjects to treatment groups
	9	Section 5.1.3 Safety laboratory parameters
	10	Section 5.2.2.1 Blood sampling for pharmacokinetic analysis

Proprietary confidential information © 2018 Boehringer Ingelheim International GmbH or one or more of its affiliated companies

Description of change	1	PK sampling schedule adapted based on SRD data; additional ECG/VS at 2h postdose
	2	Preliminary data from SRD trial 1405-0001 amended
	3	Benefit – risk assessment amended based on data gained in SRD trial.
	4	Exclusion criterion 20 more precisely described
	5	Additional criterion for individual treatment discontinuation introduced.
	6	Discontinuation of the trial by the sponsor, point 2 clarified by more detailed description.
	7	Clarification: subjects withdrawn for drug related AEs will not be replaced.
	8	Explanation that all subjects may be dosed in one cohort on the same calendar day.
	9	Test name of drug screen corrected.
	10	PK blood samples may be stored at room temperature until centrifuged.
Rationale for change	1	In the SRD trial, maximum plasma concentrations were reached earlier than expected based on preclinical data; therefore the sampling schedule for PK was adapted accordingly

2. LIST OF ABBREVIATIONS

Term	Definition / description
ADS	Analysis dataset
AE	Adverse event
AESI	Adverse event of special interest
ALT	Alanine transaminase
ANOVA	Analysis of variance
AST	Aspartate transaminase
AUC _{0-tz}	Area under the concentration-time curve of the analyte in plasma over the time interval from 0 to the last quantifiable data point
AUC _{0-∞}	Area under the concentration-time curve of the analyte in plasma over the time interval from 0 extrapolated to infinity
BI	Boehringer Ingelheim
BMI	Body mass index
BP	Blood pressure
BWC	Bioavailability/Bioequivalence, within-subject design, time-controlled
CI	Confidence interval
C _{max}	Maximum measured concentration of the analyte in plasma
CRA	Clinical research associate
CRF	Case report form
CTP	Clinical Trial Protocol
CTR	Clinical Trial Report
CV	Arithmetic coefficient of variation
DBLM	Database lock meeting
DILI	Drug induced liver injury
ECG	Electrocardiogram
EDC	Electronic data capture
EudraCT	European Union Drug Regulating Authorities Clinical Trials

Term	Definition / description
gCV	Geometric coefficient of variation
gMean	Geometric mean
ICH	International Conference on Harmonisation
iPD	Important Protocol Deviation
ISF	Investigator site file
LLT	Lower level term
Max	Maximum
MedDRA	Medical Dictionary for Regulatory Activities
Min	Minimum
N	Number non-missing observations
O*C	Oracle Clinical
P10	10th percentile
P90	90th percentile
PK	Pharmacokinetics
PKS	PK parameter analysis set
PR	Pulse rate
PT	Preferred term
Q1	1st quartile
Q3	3rd quartile
R	Reference treatment
RAGe	Report Appendix Generator system
REP	Residual effect period
RPM	Report planning meeting
SAS TM	Statistical Analysis System
SD	Standard deviation
SOC	System organ class
SOP	Standard operating procedure
T	Test treatment

Term	Definition / description
TS	Treated set
TSAP	Trial statistical analysis plan
ULN	Upper limit of normal
WHO-DD	World Health Organization Drug Dictionary
XPKISTAT	Library of SAS® Macros for PK analysis

3. INTRODUCTION

As per ICH E9 ([1](#)), the purpose of this document is to provide a more technical and detailed elaboration of the principal features of the analysis described in the protocol, and to include detailed procedures for executing the statistical analysis of the primary and secondary variables and other data.

This Trial statistical analysis plan (TSAP) assumes familiarity with the Clinical Trial Protocol (CTP), including Protocol Amendment. In particular, the TSAP is based on the planned analysis specification as written in CTP Section 7 “Statistical Methods and Determination of Sample Size”. Therefore, TSAP readers may consult the CTP for more background information on the study, e.g., on study objectives, study design and population, treatments, definition of measurements and variables, planning of sample size, randomisation.

Study data will be stored in a trial database within the Oracle ClinicalTM (O*C) system.

Pharmacokinetic (PK) parameters will be calculated using Phoenix WinNonlinTM software (version 6.3 or higher, Certara USA Inc., Princeton, NJ, USA).

The statistical analyses will be performed within the validated working environment CARE, including SASTM (current Version 9.4, by SAS Institute Inc., Cary, NC, USA), and a number of SASTM-based tools (e.g., macros for the analyses of AE data or laboratory data; Report Appendix Generator system (RAGe) for compilation/formatting of the CTR appendices).

4. CHANGES IN THE PLANNED ANALYSIS OF THE STUDY

All analyses as planned in the CTP will be performed and are described in more detail in this TSAP. No changes compared to the protocol were made.

5. ENDPOINTS

5.1 PRIMARY ENDPOINTS

Section 2.1.2 of the CTP: *The following pharmacokinetic parameters will be determined for BI 1323495:*

- AUC_{0-t_z} (area under the concentration-time curve of the analyte in plasma over the time interval from 0 to the last quantifiable data point)
- C_{max} (maximum measured concentration of the analyte in plasma)

5.2 SECONDARY ENDPOINTS

5.2.1 Key secondary endpoints

This section is not applicable as no key secondary endpoints have been defined in the CTP.

5.2.2 Secondary endpoints

Pharmacokinetic (PK):

Section 2.1.3 of the CTP: *The following pharmacokinetic parameter will be determined for BI 1323495:*

- $AUC_{0-\infty}$ (area under the concentration-time curve of the analyte in plasma over the time interval from 0 extrapolated to infinity)

There are two methods by which $AUC_{0-\infty}$ is calculated:

- AUCINF_obs: Area under the plasma concentration time curve from time zero to time infinity with extrapolated area from time t_z to infinity based on last observed concentration at time t_z
- AUCINF_pred: Area under the plasma concentration time curve from time zero to time infinity with extrapolated area from time t_z to infinity based on the concentration predicted by regression for the time t_z

Analysis will be performed on all methods available in the data.

6. GENERAL ANALYSIS DEFINITIONS

6.1 TREATMENTS

For basic study information on investigational products, assignment of treatment sequences, and selection of doses, please see CTP, Sections 3 and 4.

The study will be performed as a randomised, open-label, two-way crossover trial with two treatments (T and R) and two treatment sequences (T-R or R-T).

In total, it was planned to assign 12 healthy male subjects to the two treatment sequences in a 1:1 ratio.

For details of dosage and formulation see Table 6.1: 1 below:

Table 6.1: 1 Treatments and labels used in the analysis

Treatment		Short label	Short label for footnote
T fed	tablets of BI 1323495,	BI fed	BI 1323495 fed
R fasted	tablets of BI 1323495,	BI fasted	BI 1323495 fasted

The following separate study phases will be defined for the analyses of AEs:

- **Screening** (ranging from 0:00 h on day of informed consent until first administration time of study drug)
- **On treatment** (separately for each treatment, ranging from the time of administration of the respective treatment until next drug administration of 0:00 h or on the day after trial termination date)

Please note that all AEs reported between start of trial drug administration and the last per-protocol contact will be considered on treatment (i.e. no follow-up period is considered in this trial).

Displays of AEs will be presented separately for the treatments described in [Table 6.1: 1](#) above.

For detailed information on the handling of the treatments in the O*C views refer to Technical TSAP ADS plan and Data Reviewers guide.

6.2 IMPORTANT PROTOCOL DEVIATIONS

Data discrepancies and deviations from the CTP will be identified for all treated subjects.

Consistency check listings (for identification of deviations of time windows) and a list of protocol deviations (e.g. deviations in drug administration, in blood sampling times, etc.) will be provided to be discussed at the combined report planning and database lock meeting (RPM/DBLM). At this meeting, all manual deviations identified at the sites by the CRAs and deviations too complex to program will be reviewed by the trial team to decide which are considered important. For definition of important protocol deviations (iPD), and for the process of identification of these, refer to the Boehringer Ingelheim (BI) SOP "Identify and Manage Important Protocol Deviations (iPD)" (2).

If any iPDs are identified, they are to be summarised into categories and will be captured in the RPM minutes via an accompanying Excel spreadsheet (3).

For a description of categories which are considered to be iPDs in this trial, please refer to the IQRM plan.

6.3 SUBJECT SETS ANALYSED

- Treated set (TS):
This subject set includes all subjects who were dispensed study medication and were documented to have taken at least one dose of study drug.
This is the full analysis set population in the sense of ICH-E9 (1).
It is used for safety analyses.

Section 7.3 of the CTP: *Plasma concentration data and parameters of a subject will be included in the statistical pharmacokinetic (PK) analyses if they are not flagged for exclusion due to a protocol violation relevant to the evaluation of PK (to be decided no later than in the Report Planning Meeting) or due to PK non-evaluability (as revealed during data analysis, based on the criteria specified below). Exclusion of a subject 's data will be documented in the CTR.*

Relevant protocol violations may be

- *Incorrect trial medication taken, i.e. the subject received at least one dose of trial medication the subject was not assigned to*
- *Incorrect dose of trial medication taken*
- *Use of restricted medications*

Plasma concentrations and/or parameters of a subject will be considered as non-evaluable, if for example

- *The subject experienced emesis that occurred at or before two times median t_{max} of the respective treatment (Median t_{max} is to be determined excluding the subjects experiencing emesis)*
- *A predose concentration is $>5\% C_{max}$ value of that subject*

- *Missing samples/concentration data at important phases of PK disposition curve*
- PK parameter analysis set (PKS):
This subject set includes all subjects in the TS who provide at least one primary or secondary PK parameter that was not excluded according to the description above. Thus, a subject will be included in the PKS, even if he contributes only one PK parameter value for one period to the statistical assessment.

The descriptive analysis of PK concentrations will be based on the ADS ADPC as described at the beginning of [Section 7](#).

The following [Table 6.3: 1](#) contains the information which subject is used for which class of endpoint:

Table 6.3: 1 Subject sets analysed

Class of endpoint	Subject set	
	TS	PKS
Analyses of primary and secondary PK endpoints		X
Safety endpoints	X	
Demographic/baseline endpoints	X	
Important protocol deviations	X	
Disposition	X	

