1.4 BENEFIT - RISK ASSESSMENT

Participation in this clinical trial is without any (therapeutic) benefit for healthy subjects. Their participation, however, is of major importance for the development of a new orally available drug, which might improve the therapy in patients with COPD and emphysema. The subjects are exposed to the risks of the study procedures and the risks related to the exposure to the trial medication.

Procedure-related risks

The use of an indwelling venous catheter or venepuncture for e.g. blood sampling may result in mild bruising, and in rare cases, in transient inflammation of the wall of the vein, or nerve injury, potentially resulting in paraesthesia, reduced sensibility, and/or pain for an indefinite period.

The total volume of blood withdrawn per subject during the entire study will not exceed the volume of a normal blood donation (500 mL). No health-related risk to healthy subjects is expected from withdrawal of this volume of blood.

Drug-related risks and safety measures

In this food effect trial, subjects will receive two single doses of _____ once under fasted and once under fed conditions. Administration of BI 1323495 under fed conditions may cause an increase of plasma concentrations of BI 1323495. However, based on modelling data for the tablet formulation used in the SRD trial and this food effect trial only a minimal food effect is expected for a dose of _____ resulting in plasma concentrations below those exposures seen in the SRD trial following doses of _____ and above.

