4.1.1 Identity of the Investigational Medicinal Products

The characteristics of the test product are given below:

Substance: BI 1323495

Pharmaceutical formulation: Tablet, film-coated

Source: BI Pharma GmbH & Co. KG, Germany

Unit strength:

Posology: 2-0-0

Route of administration: oral

Duration of use: single dose in treatment T and R

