4.1.4 Drug assignment and administration of doses for each subject

This trial is a 2-way crossover study. All subjects will receive the 2 treatments in randomised order. The treatments to be evaluated are outlined in Table [4.1.4: 1](#) below.

Table 4.1.4: 1 Dosage and treatment schedule

Treatment	Substance	Formulation	Unit strength	Dosage	Total dose
T (Test)	BI 1323495	Tablet, film-coated		as single dose, fed state	
R (Reference)	BI 1323495	Tablet, film-coated		as single dose, fasted state	

Administration of trial medication will be performed after subjects have fasted overnight; fasting is to start no later than 10 h before the scheduled dosing.

In treatment T, a high-fat, high-calorie meal will be served within 30 min before drug administration. The subjects must completely consume the meal prior to drug intake. The composition of the standard high-fat, high-calorie meal is detailed in Table [4.1.4: 2](#); this meal is in compliance with the FDA guidance ‘Food-Effect Bioavailability and Fed Bioequivalence Studies’ ([R03-2269](#)). For restrictions with regard to diet, see Section [4.2.2.2](#).

Table 4.1.4: 2 Composition of the high-fat, high-calorie meal

Ingredients	kcal
2 chicken eggs (whole content) for scrambled eggs	192
10 g butter for frying scrambled eggs	75

Proprietary confidential information © 2018 Boehringer Ingelheim International GmbH or one or more of its affiliated companies

Ingredients	kcal
35 g fried bacon	186
2 toasted slices of wheat bread	130
15 g butter for buttering toast slices	113
115 g hash brown potatoes	132
240 mL whole milk (3.5% fat)	156
Sum¹	984

¹ The total caloric content was supplied approximately as following: 150 kcal as protein, 250 kcal as carbohydrate, and 500 to 600 kcal as fat.

The investigator (or authorised designee) will administer the trial medication as an oral dose together with about 240 mL of water to subjects who are in a standing position. For drug administration, the so-called four-eye principle (two-person rule) should be applied. For this, one authorised employee of the trial site should witness the administration of trial medication, and – if applicable – its preparation (e.g. reconstitution), if correct dosage cannot be ensured otherwise.

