4.1.5 Blinding and procedures for unblinding

This Phase I trial will be handled in an open fashion throughout (that is, during the conduct, including data cleaning and preparation of the analysis). This is considered acceptable because the potential for bias seems to be low and does not outweigh practical considerations.

Emergency envelopes will not be provided, because the dose of trial medication is known to investigators and subjects.

PK samples will be labelled in such a way that treatment allocation cannot be derived by the analytical site.

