7.3.4 Safety analyses

Safety will be analysed based on the assessments described in Section [2.2.2.2](#). All treated subjects (TS, refer to Section [7.3](#)) will be included in the safety analysis. Safety analyses will be descriptive in nature and based on BI standards. No hypothesis testing is planned.

For all analyses, the treatment actually administered (= treatment at onset) to the subject will be used (any deviations from the randomised treatment will be discussed in the minutes of the Report Planning Meeting).

Treatments will be compared in a descriptive way. Tabulations of frequencies/proportions will be used to evaluate categorical (qualitative) data, and tabulations of descriptive statistics will be used to analyse continuous (quantitative) data.

Measurements (such as ECG, vital signs, or laboratory parameters) or AEs will be assigned to treatments (see Section [4.1](#)) based on the actual treatment at the planned time of the measurement or on the recorded time of AE onset (concept of treatment emergent AEs). Therefore, measurements planned or AEs recorded prior to first intake of trial medication will be assigned to the screening period, those between first trial medication intake and end of trial termination date will be assigned to the treatment period. These assignments including the corresponding time intervals will be defined in detail in the TSAP. Note that AEs occurring after the last per protocol contact but entered before final database lock will be reported to Pharmacovigilance only and will not be captured in the trial database.

Additionally, further treatment intervals (analysing treatments) may be defined in the TSAP in order to provide summary statistics for time intervals, such as combined treatments, on-treatment totals, or periods without treatment effects (such as screening and follow-up intervals).

Adverse events will be coded using the Medical Dictionary for Regulatory Activities (MedDRA). Frequency, severity, and causal relationship of AEs will be tabulated by treatment, system organ class, and preferred term. SAEs, AESIs (see Section [5.2.5.1](#)), and other significant AEs (according to ICH E3) will be listed separately.

Previous and concomitant therapies will be presented per treatment group without consideration of time intervals and treatment periods.

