7.4 PRIMARY ENDPOINTS

Relative bioavailability of BI 1323495 is to be determined on the basis of the primary and secondary pharmacokinetic endpoints (see [Section 5.1](#)).

Section 7.3.1 of the CTP:

Primary analysis

The statistical model used for the analysis of primary and secondary endpoints will be an analysis of variance (ANOVA) model on the logarithmic scale. That is, the PK endpoints will be log-transformed (natural logarithm) prior to fitting the ANOVA model. This model will include effects accounting for the following sources of variation: sequence, subjects within sequences, period and treatment. The effect ‘subjects within sequences’ will be considered as random, whereas the other effects will be considered as fixed. The model is described by the following equation:

$$y_{ijkm} = \mu + \zeta_i + s_{im} + \pi_j + \tau_k + e_{ijkm}, \text{ where}$$

y_{ijkm} = logarithm of response measured on subject m in sequence i receiving treatment k in period j,

μ = the overall mean,

ζ_i = the ith sequence effect, i = 1, 2

s_{im} = the effect associated with the mth subject in the ith sequence, m = 1, 2, ..., 6

π_j = the j^{th} period effect, $j = 1, 2$

τ_k = the k^{th} treatment effect, $k = 1, 2$

e_{ijkm} = the random error associated with the m^{th} subject in sequence i who received treatment k in period j .

The implementation for this analysis will be accomplished by using the XPKISTAT macro, based on PKS, and option BWC (Bioavailability/Bioequivalence, within-subject design, time-controlled).

Section 7.3.1 of the CTP: *For each endpoint, the difference between the expected means for $\log(T)-\log(R)$, will be estimated by the difference in the corresponding adjusted means (Least Squares Means). Additionally, their two-sided 90% confidence intervals will be calculated based on the residual error from the ANOVA and quantiles from the t-distribution. These quantities will then be back-transformed to the original scale to provide the point estimate and 90% CIs for each endpoint.*

Further exploratory analyses

As a sensitivity analysis, this ANOVA will be repeated for the primary and secondary endpoints with all sources of variation ('sequence', 'subjects within sequences', 'period', 'treatment') considered as fixed effects. This analysis will be done using PROC GLM.

The following SAS code can be used to fit the model:

```
PROC GLM DATA=indata;
  CLASS subject treatment sequence period;

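### Do the PK exclusion rules need a listed item for a wrong or incomplete fed/fasted state?

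*SAP*

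**What the plan says.** SAP 6.3 takes its exclusion rules from protocol 7.3. The PK-relevant violations are introduced as things that *may* be relevant, and there are three: "Incorrect trial medication taken, i.e. the subject received at least one dose of trial medication the subject was not assigned to", an incorrect dose, and use of restricted medications. The non-evaluability criteria are given as examples: early emesis, a predose concentration above 5% of Cmax, and missing samples at important phases.

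Protocol 4.1.1 describes one product for both arms ("Duration of use: single dose in treatment T and R"). Protocol 4.1.4 then sets the prandial conditions. For both treatments, "Administration of trial medication will be performed after subjects have fasted overnight". For the test treatment a high-fat meal is added, and "The subjects must completely consume the meal prior to drug intake".

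The model in SAP 7.4 defines the response as "logarithm of response measured on subject m in sequence i receiving treatment k in period j". Protocol 7.3.4, on safety, says "the treatment actually administered (= treatment at onset) to the subject will be used". On deviations, SAP 6.2 has them identified for all treated subjects, names drug administration among the examples, and takes them to the combined report planning and database lock meeting. For the list of categories it points to the IQRM plan, whereas protocol 7.3 said that categories would be suggested in the SAP.

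**The concern.** The fed or fasted state is the only thing the primary ratio compares, yet none of the six listed items names it. The item that looks designed to catch a wrong treatment is worded in terms of medication, and every subject is assigned the same medication in both periods. Read that way, it is empty.

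The explicit rule to analyse by treatment actually given stands only in the safety section. A reader may therefore ask under which label a swapped period enters the PK model.

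The trial is also open "during the conduct, including data cleaning and preparation of the analysis". A choice to keep, exclude or relabel a period would be made case by case by people who know the allocation, in an estimate resting on 12 subjects. If a period without food were analysed as fed, the ratio would be pulled towards 1.

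**Working it through.** **Reading the text.** Three situations need separating.

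| Event | Covered by a listed item? | Route in the plan |
|---|---|---|
| Full swap (fed dose in a fasted period, or the reverse) | Yes, if medication is read as treatment | Listed item; SAP 6.2 review; model indexed by treatment received |
| Test meal not finished | No | Open list; SAP 6.2 review |
| Fast broken before the reference dose | No | Open list; SAP 6.2 review |

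The first row turns on wording. The protocol's abbreviation list defines T as the test product or treatment. The dosage table in protocol 4.1.4 puts the fed or fasted state in the Dosage column, in a section headed as drug assignment. Subjects are assigned to a sequence, so a period has an assigned treatment. On that ordinary reading, a fed dose in a reference period is one the subject was not assigned to. The claim that the item can never be met needs the narrower reading.

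On labelling, the model refers to the treatment the subject is receiving, and SAP 7 sorts the listings by actual treatment. Both point to analysis by condition received.

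**Size if a wrong period were kept.** The documents state no expected ratio and no coefficient of variation (CV), so there is no planned figure to reproduce. Inputs from the documents are 12 subjects, 1:1 allocation (6 per sequence), a log scale and a 90% interval. True ratios θ are assumed. Values of 1.05 and 1.10 are used because protocol 1.4 says "only a minimal food effect is expected"; 1.25 is added as a larger case.

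In the balanced two-period crossover each subject's within-subject difference has weight 1/12 in the estimated log ratio.

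- One test period taken without the meal but kept as test: that subject's expected difference is 0 instead of log θ. The expected estimate is θ^(11/12).
- Both periods of one subject swapped but analysed as randomised: that difference is −log θ. The expected estimate is θ^(10/12).

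| Assumed θ | One unfed test period kept | Change | Full swap, as randomised | Change |
|---|---|---|---|---|
| 1.05 | 1.046 | −0.4% | 1.041 | −0.8% |
| 1.10 | 1.091 | −0.8% | 1.083 | −1.6% |
| 1.25 | 1.227 | −1.8% | 1.204 | −3.6% |

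**Against the precision of the estimate.** With an assumed within-subject CV of 30%, σ_w = √ln(1 + 0.30²) = 0.294. The 90% half-width on the log scale is t(0.95; 10) × σ_w × √(1/6) = 1.812 × 0.294 × 0.408 = 0.217, or about +24%/−20% on the ratio. The bias from one unfed test period is log θ / 12:

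- θ = 1.05: 0.0488 / 12 = 0.0041, which is 1.9% of the half-width.
- θ = 1.10: 0.0953 / 12 = 0.0079, which is 3.7% of the half-width.

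A full swap analysed as randomised doubles these, to 3.7% and 7.3%.

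**What excluding a period does.** Dropping one test period while keeping that subject's reference period moves the log ratio by 11% to 14% of the half-width on average, and by 27% to 34% at two standard deviations (assumed within-subject CV 20% to 40%, between-subject CV 20% to 80%). This is not bias. It is the sampling shift from losing any test period, and a missed visit or emesis would produce the same. The standard error grows by about 4% (assumed CVs 30% within, 50% between).

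**The case for a change.** The strongest case for a change is that an open list permits the team to act without telling it what to do. Emesis and wrong dose are listed even though dosing is supervised, so low likelihood is no reason to leave out the one factor under study. Blinded bioanalysis protects the assay, not the decision to keep or exclude a period. A few sentences would settle the matter at no cost in data.

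Part of this stands. Neither document presets an outcome for an unfinished meal or a broken fast, and an added example would be harmless. It would not clearly improve the analysis, however. A rule to exclude any incompletely fed period needs a threshold, since otherwise a small remnant of the meal deletes one of 12 test periods. Keeping such periods as assigned is equally defensible. That is a trade-off, not the correction of an error. Nor can it be said that no rule exists: SAP 6.1, 6.2 and 7 defer to the ADS plan, the IQRM plan and the sponsor's non-compartmental analysis standard, none of which is available here.

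The difference over where deviation categories are listed (protocol 7.3 against SAP 6.2, with SAP 4 declaring no changes) is real. It concerns the location of a list and alters no result.

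**Conclusion.** The narrow observation is correct: no listed item names the meal or the fast. The stronger claim, that the first item cannot be met, depends on a literal reading that the protocol's own usage does not support. Following the plan as written produces no wrong result. Deviations from the meal and fasting requirements fall within the SAP 6.2 review, have to be judged for PK relevance no later than the report planning meeting, and the model takes the treatment received.

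The event is also unlikely. Subjects unable to follow the diet are excluded (criterion 19), food on site is supplied by staff, subjects are admitted the evening before, complete consumption is required before drug intake, and dosing is supervised.

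If one unfed test period did slip through, the ratio would be biased by 0.4% to 0.8%. A full swap analysed as randomised would bias it by 0.8% to 1.6%. Both rest on assumed true ratios of 1.05 to 1.10 and one affected subject in 12. A larger food effect would raise them, to 1.8% and 3.6% at 1.25. In an exploratory trial with no acceptance range, this is missing detail that the team can fill sensibly, and no change is called for.
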